5.2.3 Full Analysis Set (FAS)

The FAS population will consist of all randomized/enrolled subjects who received at least one dose of study drug and have at least one post-dose Hb assessment. If treatment received differs from the randomized treatment, the randomized treatment assignment will be used for efficacy analysis.

5.2.4 Per Protocol Set (PPS)

The PPS population will consist of all subjects in the FAS population who received at least 8 weeks of treatment, have at least one valid post-dose Hb assessment and are without major protocol violations.

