### 8.2 Analysis Populations

The following analysis populations will be used for the statistical analysis:

- Safety Population: The Safety Population consists of all subjects who received at least one dose of study treatment. All safety data will be tabulated using descriptive statistics. If treatment received during the study differs from the randomized treatment, the actual treatment arm will be used for the analysis.

- Intent-to-Treat population: The ITT population consists of all randomized subjects. The primary efficacy endpoint for the US (FDA) submission will be analyzed using this population. In addition, the superiority comparison of this endpoint for the US (FDA) submission will be performed using this population as well.
- Full Analysis Set: The FAS consists of all subjects who receive at least one dose of study drug and have at least one postdose Hb assessment. If treatment received differs from the randomized treatment, the randomized treatment arm will be used. Efficacy analysis for superiority will be conducted on the FAS population for the EMA submission.
- Per Protocol Set: The PPS consists of all randomized subjects who received at least 4 weeks of study treatment, have at least one postdose Hb assessment and are without major protocol violations. Criteria for PPS exclusion will be defined in the Statistical Analysis Plan (SAP). Non-inferiority analyses for the EMA submission will be based on the PPS.

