### **8.4.5 Statistical Analysis Plan**

The Statistical Analysis Plan will provide details of the data analyses. As an open-label study the SAP will be finalized prior to accumulation of a substantial amount of data to ensure lack of bias. Any significant changes to the analyses described in this protocol will be highlighted in the SAP and the Clinical Study Report.

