1 INTRODUCTION

This statistical analysis plan (SAP) provides a more technical and detailed elaboration of the statistical analyses of efficacy and safety as outlined and/or specified in the final study protocol. Specifications of tables, figures, and data listings are contained in a separate document (Table shells).

A separate pooled-analysis SAP for pre-specified analysis based on adjudicated composite safety data will complement this study specific SAP. This SAP is based on the Amendment 4 of the protocol dated September 20, 2017.

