5.2.5 Major Protocol Deviations

Major protocol deviations of interest may include, but are not limited to the criteria in Table 2.

A subset of pre-specified major protocol deviations will exclude some patients in the PPS analyses. These will be identified while data are collected prior to database lock. Considerations will be given according to the following table.

Table 2. Criteria for Assessing Major Protocol Deviations

Number	Major Protocol Deviation
1	Violation of key* inclusion or exclusion criteria which may affect the assessment of the efficacy of the study drug
2	Administration of wrong randomization study drug for more than 4 week before week 24; any duration from week 24 to week 52
3	Study drug compliance < 75% (up to Week 52)
4	Administration of prohibited concomitant medication that may impact evaluation of efficacy of the study drug*
5	Significant noncompliance with study procedures that may impact evaluation of efficacy of the study drug will be evaluated case by case*

*Subject to Medical Monitor's decision

The number and percentage of major protocol deviations will be categorized and summarized by treatment group as deemed appropriate.

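### The Ex-US primary non-inferiority test rests on a PPS that needs 8 weeks of treatment in the SAP but 4 in the protocol, and no supportive analysis outside the PPS is designated for that claim

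*SAP*

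**What the plan says.** **Minimum treatment.** Protocol 8.2 builds the PPS from "all randomized subjects who received at least 4 weeks of study treatment", with a post-dose Hb value and no major violation. SAP 5.2.4 starts from the FAS and takes those "who received at least 8 weeks of treatment, have at least one valid post-dose Hb assessment and are without major protocol violations". The two texts are meant to match. SAP 1 states: "This SAP is based on the Amendment 4 of the protocol dated September 20, 2017". Protocol 8.4.5 adds: "Any significant changes to the analyses described in this protocol will be highlighted in the SAP and the Clinical Study Report". The SAP does not flag the move from 4 to 8 weeks.

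**Deviations.** Protocol 8.2 leaves the PPS exclusion criteria to the SAP. SAP 5.2.5 offers an open list (Table 2) and says: "A subset of pre-specified major protocol deviations will exclude some patients in the PPS analyses". The subset is not named. It is to be identified during data collection and before database lock. Rows 1, 4 and 5 are at the Medical Monitor's decision. Row 2 reads "Administration of wrong randomization study drug for more than 4 week before week 24; any duration from week 24 to week 52". Row 3 is compliance below 75% up to Week 52.

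**Use of the set.** SAP 11.1.2 assigns Ex-US NI to the PPS and Ex-US superiority to the FAS. The logistic repeat in 11.1.3.3 is again on the PPS. SAP 11.1.2 counts subjects who drop out without data for the assessment as non-responders. SAP 6 tabulates PPS exclusions by reason and arm.

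**The concern.** The two documents define different analysis sets for one of the two primary claims. The subjects affected are those who stop between Weeks 4 and 8. If they have not responded, the protocol rule keeps them as failures and the SAP rule removes them. In an open-label trial the numbers stopping early may differ by arm, so the choice of rule can move the estimated difference.

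Two things make this harder to judge afterwards. First, the list of excluding deviations is not closed. If Table 2 rows 2 and 3 are on it, conduct between Weeks 24 and 52 can remove a subject whose 24-week outcome is already fixed. That later window fits the Ex-US Hb-change secondary, whose own window is given as Weeks 28 to 36 in SAP 4.3 and Weeks 28 to 52 in Table 5. Only one PPS is defined for both endpoints. Second, nothing in the Ex-US analysis is designated to show whether NI holds without the exclusions. The table in SAP 6 would show uneven exclusions, but not their effect on the conclusion.

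**Working it through.** **Inputs from the documents.** Planned response 80% in both arms, margin -15 points, two-sided 95% CI, at least 600 subjects at 1:1, so 300 per arm (SAP 5.1, SAP 3). SAP 5.1 also mentions about 1000 subjects, so 500 per arm. Neither document gives a PPS exclusion rate.

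**The plan's power.** With R for roxadustat and E for epoetin, P(NI) = Φ((pR − pE + 0.15)/SE − 1.96), where SE = √(pR(1−pR)/nR + pE(1−pE)/nE). At 300 per arm, SE = √(0.32/300) = 0.0327, 0.15/0.0327 = 4.59, and Φ(4.59 − 1.96) = 99.6%. This agrees with the stated 99% or more; 262 per arm would be enough for 99%.

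**Effect of the 4- to 8-week gap.** Assumptions: true rates on the protocol set of 65% and 80%, which is the NI null, and every subject removed is a non-responder. Exclusions are percentages of the whole arm. Response rates and arm sizes are recomputed after removal. Example, 4% vs 2% at 300 per arm: 195/288 = 67.7% and 240/294 = 81.6%, difference −13.9, SE 0.0356, Φ(0.30 − 1.96) = 4.9%.

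| Excluded, R vs E | Difference (points) | P(NI), 300 per arm | P(NI), 500 per arm |
|---|---|---|---|
| none | −15.0 | 2.5% | 2.5% |
| 2% vs 2% | −15.3 | 2.0% | 1.9% |
| 2% vs 1% | −14.5 | 3.5% | 3.8% |
| 1% vs 2% | −16.0 | 1.3% | 1.0% |
| 4% vs 2% | −13.9 | 4.9% | 5.8% |

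Simulation of 400,000 trials per row with the unstratified Miettinen-Nurminen test agreed to within about 0.1 point.

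**Break-even.** With 2% removed from roxadustat, the difference stays at −15 if epoetin's rate becomes 0.65/0.98 + 0.15 = 0.8133, so epoetin loses 1 − 0.80/0.8133 = 1.63%. Below that the SAP rule favours NI; above it, the reverse.

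**Softer assumption.** If half of those removed are non-responders and half are unrelated to response, 4% vs 2% gives 3.5% (300 per arm) or 3.9% (500 per arm). If all are unrelated, it stays at 2.5%.

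**At the planned rates.** With 80% in both arms and 300 per arm, the four exclusion cases give 99.3% to 99.96%, against 99.6% with none.

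**Compliance to Week 52 (mechanism only).** Take the dose-ratio measure in SAP 9.2 and a constant weekly dose. A subject 90% compliant to Week 24 is removed if later compliance c satisfies (24×0.90 + 28c)/52 < 0.75, so c < 62.1%. A subject 60% compliant to Week 24 stays if (24×0.60 + 28c)/52 ≥ 0.75, so c ≥ 87.9%. Protocol 1.6 expects a 22 to 35% weekly dose reduction for maintenance. If that fell at Week 24 (an assumption), the 28 later weeks carry weight 28×0.78 = 21.84 or 28×0.65 = 18.2. The thresholds become 58.5% or 55.2%, and 91.5% or 94.8%.

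**The case against.** The strongest reply is that a non-PPS result will exist. The US first secondary tests the same 24-week response for NI by the same method (SAP 11.2.1.1), with a 0.15 margin (Table 5), on the ITT in SAP 4.3 or the FAS in SAP 11.2.1. An Ex-US superiority analysis on the FAS is also assigned. This stands. A reader might infer that no NI test outside the PPS is specified anywhere, and the documents do not support that. What is missing is a designation: the US run is a step in the US sequence, its population is stated two ways, and it is not named as support for the Ex-US claim. The sensitivity definition in SAP 4.2.1 does not fill the gap, because it disregards rescue and names no analysis set.

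Second, the size is modest. The largest inflation shown needs twice as many exclusions on roxadustat and every one a non-responder. Some who stop in Weeks 4 to 8 could already have responded: early visits are weekly, and Protocol 1.4.2.2 reports a mean rise of about 2 g/dL after 6 weeks. This also stands, and it is why the half-and-half case is shown.

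Third, the Week 52 point is conditional on an unnamed subset. The compliance thresholds depend on a constant dose and on one of two measures in SAP 9.2, and Table 2 does not say which measure applies. This stands too; the thresholds show how a subject could be removed, not how many would be.

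Fourth, safeguards exist: identification before lock and a table of exclusions by arm. They help, but nothing requires the decisions to be made without reference to arm or response.

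**Conclusion.** The 4- versus 8-week difference is a plain inconsistency in the analysis set of the Ex-US primary test. It should be fixed, along with the missing supportive designation. The open list of excluding deviations adds to it. Confidence is high on the inconsistency and on the unnamed subset. The Week 52 point holds only if rows 2 and 3 exclude.

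Under the assumed exclusion rates, P(NI) at the null runs from about 1.0% to 5.8% against a nominal 2.5%. At the planned rates it stays at or above 99.3%. The gap therefore matters if the true difference is near the margin, and little otherwise.

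A reader might infer that the SAP rule tilts the test towards NI, or that the stated power is wrong. Neither follows. The direction depends on how many responders and non-responders leave each arm, which the documents do not give; equal exclusions of non-responders make the test stricter. The power figure reproduces.

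**What to change.** 1. State one minimum-treatment rule for the PPS in both documents. If the SAP rule is to differ from the protocol, flag it there as a change, as Protocol 8.4.5 requires.
2. Specify the same -15% Miettinen-Nurminen NI test on the FAS, with dropouts as non-responders, as the supportive analysis for the Ex-US primary.
3. If Table 2 rows 2 and 3 exclude subjects, say so, and assess them only from first dose to Week 24 for the Ex-US primary PPS. Set any later-window flag for the Hb-change secondary after the windows in SAP 4.3 and Table 5 are reconciled.
4. Require the pre-lock exclusion decisions to be made without reference to arm or Hb response.

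The cost is SAP wording and possibly a second PPS flag. If the planned FAS superiority comparison uses the same interval, its lower bound only has to be read against -15%; otherwise it is one extra run. The downside is that some later non-compliers stay in the primary PPS. Selection between an early response and Week 24 also remains, so item 3 reduces the problem without removing it.

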5.2.5 Major Protocol Deviations

Major protocol deviations of interest may include, but are not limited to the criteria in Table 2.

A subset of pre-specified major protocol deviations will exclude some patients in the PPS analyses. These will be identified while data are collected prior to database lock. Considerations will be given according to the following table.

Table 2. Criteria for Assessing Major Protocol Deviations

Number	Major Protocol Deviation
1	Violation of key* inclusion or exclusion criteria which may affect the assessment of the efficacy of the study drug
2	Administration of wrong randomization study drug for more than 4 week before week 24; any duration from week 24 to week 52
3	Study drug compliance < 75% (up to Week 52)
4	Administration of prohibited concomitant medication that may impact evaluation of efficacy of the study drug*
5	Significant noncompliance with study procedures that may impact evaluation of efficacy of the study drug will be evaluated case by case*

*Subject to Medical Monitor's decision

The number and percentage of major protocol deviations will be categorized and summarized by treatment group as deemed appropriate.

5.3 METHODOLOGY AND CONVENTIONS

Safety and efficacy data will be summarized and presented by treatment group and time point in summary tables. Continuous variables will be presented by descriptive statistics: n, mean, standard deviation, median, minimum, and maximum. Categorical variables will be tabulated by frequency count and percentage.

Lab results obtained from the central laboratory, rather than local laboratories, will be used for all efficacy and safety analyses. Local laboratory values, if collected in the CRF's, will be listed only in data listing.

When the actual treatment received by a subject is different from the randomized treatment assigned, the subject will be analyzed per the randomized treatment for the efficacy parameters; while they will be analyzed per actual treatment that was taken for the safety parameters for US submission.

Unless otherwise stated, all statistical tests will be two-sided hypothesis tests performed at the 5% level of significance for main effects and all confidence intervals will be two-sided 95% confidence intervals.

The secondary endpoints will be tested sequentially using the fixed sequence approach for multiplicity adjustments at an alfa level of 0.05. There will be no adjustments for multiple comparisons for other tests.

All analyses will be performed using SAS® Version 9.1.3 or higher.

5.4 ADDITIONAL DATA HANDLING RULES AND PRESENTATION SPECIFICATIONS

The following general guidelines will apply to all statistical analyses and data presentations:

- Baseline is defined as the last available value obtained prior to the first dose of study drug, unless otherwise specified in this SAP.
- Hb baseline is defined as the mean of the at least last three available values obtained prior to the first dose.
- Baselines for reticulocyte count, reticulocyte hemoglobin content (CHr), hepcidin, serum iron parameters (transferring, TIBC, TSAT, Ferritin, sTfR, and iron), lipids, blood pressures and heart rate are defined as the mean of values obtained within 6 weeks prior to the first dose.
- Randomization stratification factors and enrollment protocol version derived from actual data (not the ones from the randomization system) will be used in all applicable analysis models.

The stratification factors to be used in efficacy analyses are:

1. Us vs Ex-US Screening Hb values (≤ 8 g/dL vs. > 8 g/dL) (other than Hb related endpoints)
2. Cardiovascular/cerebrovascular/thromboembolic medical history (Yes vs. No)
3. Geographic Region
4. The original protocol and amended protocols

- Unscheduled visits within an allowable window will be grouped into the closest scheduled visits based on the visit window specified in Appendix 1. For subjects who have more than one measurement at a certain scheduled visit, the last measurements

will be used, with the exception of CPK, WBC, liver function tests (i.e., ALT, AST, GGT, ALP, and total bilirubin), in which the maximum measurement will be used.

- By default, US conventional units will be used for laboratory value presentations. A set of lab summary tables in SI units will also be provided based on TLF index.
- Age is calculated as of date that the informed consent form was signed.
 - age = INTCK('YEAR', Birth date, date of Informed Consent, 'C') where INTCK is a SAS function.
- Duration of treatment or days in treatment is calculated as: last dose date – first dose date +1
- Body weight, height and temperatures will be converted using the following formula:
 - kg = lb/2.2
 - cm = 2.54 x in
 - C° = (5/9) x (F° – 32)
- The mean, standard deviation and median will be presented with adding one more decimal to raw data with rounding off. The minimum and maximum will be presented with the same number of decimals as in the raw data.
- All percentages will be rounded to one decimal place and lined up by the decimal place. The percentage will be suppressed when the count is zero.
- Any p-values will be rounded to four decimal places and will be presented as '<.0001' if they are less than 0.0001 after rounding.
- All tables and listings will have a header showing "FibroGen, Inc.", the protocol number, and Page x of y. Footer will indicate the program file path/name, run date and run time.
- For continuous variables that are recorded as "< X" or "> X", the value of "X" will be used in the calculation of summary statistics. The original values will be used for the listings.
- Decimal points will be presented as follows: N will be presented without decimal, minimum and maximum in same precision as in the database, mean and median in one more decimal than minimum and maximum, and SD in one more decimal than mean and median.
- Tables and figures will use derived analysis visit. Listings will use nominal visits, show the flag to indicate analysis visit to be used. Namely, both Nominal visit and analysis visit will be presented in the listing.
- Additional data handling conventions are detailed in Appendix 1.

6 SUBJECT ACCOUNTABILITY AND DISPOSITION

The following subject data will be summarized and presented by treatment group (roxadustat and active control) if applicable:

- Number and percentage of subjects screened and randomized (using the screened subjects population)
- Number and percentage of subjects randomized at each center, and for all centers combined, by treatment group (using the ITT population)
- Number and percentage of subjects in each analysis set, by treatment group (using the ITT population)

- Number and percentage of subjects excluded from the Per Protocol analysis set by reason for exclusion, treatment group (using the ITT population)
- Kaplan-Meier plots will be generated for premature treatment discontinuation by randomization arm showing 2 curves (one curve per treatment group).
- All subjects who prematurely discontinued during the treatment period will be listed by discontinuation reason for the randomized population.

7 DEMOGRAPHICS AND OTHER BASELINE CHARACTERISTICS

Demographic parameters and important baseline and disease characteristics will be summarized by treatment group for the ITT, Safety, FAS and PPS populations. These include but may not be limited to age, age group (18 to 64, 65 to 74, ≥ 75), sex, ethnicity, race, region, weight, body-mass index (BMI), Hemoglobin, baseline Hb categories, iron repletion status at baseline, Ferritin, Ferritin group (<100 vs. ≥ 100 ng/mL), TSAT and TSAT group ($<20\%$ vs. $\geq 20\%$), iron deplete (ferritin ≥ 100 and TSAT $\geq 20\%$) vs. not, cHepcidin $<$ eligibility threshold or not, baseline C-reactive protein (CRP) group (CRP \leq ULN vs. CRP $>$ ULN), cardiovascular or cerebrovascular or thromboembolic medical history (yes vs. no), primary reason for CKD/ESRD as one of the baseline characteristics (DM and HPT vs. all others).

In addition, 25%-75% values of Hb and platelets will be presented. Frequency distributions (number and percentage of subjects) will be presented for categorical variables.

The baseline characteristics, iron indices, and iron IV given between ESA naïve and those treated with ESA then washed out will be summarized and presented in a table.

Descriptive statistics of baseline values for other parameters will be presented in their change from baseline tables.

A summary table for the patient population for enrolled patients before and after the protocol amendments will be presented.

8 MEDICAL HISTORY

Medical history will be coded using Medical Dictionary for Regulatory Activities (MedDRA). Medical History of interest including Chronic Kidney Disease (CKD) History inclusive of CKD Cause, Cardiovascular Disease, Cerebrovascular Disease, Thrombosis History, Hypertension History, Diabetes History, and Anemia History will be summarized by system organ class, preferred term and treatment group for the Safety Population.

9 STUDY MEDICATION

9.1 EXTENT OF EXPOSURE

Exposure to study medication will be summarized by treatment group in terms of treatment duration in weeks, which is calculated using the following formula: (the date of last medication taken - the date of first dose taken +1)/7.

Total weekly study drug exposure is defined as the total prescribed dose (in mg and mg/kg for Roxadustat and IU and IU/kg for EPO) of study drug administered within the week (windowed by 7-day period from Day 1).

Duration of exposure, weekly exposure and total study drug exposure will be tabulated by treatment group for the safety population.

Per administration amount and administration frequency will also be tabulated by treatment group for the safety population and PPS population.

Patient-Exposure-Year (PEY) is defined as (Last Dose Date – First Dose Date + 1)/365.25.

9.1.1 Dosing Changes

Dosing changes for both treatment groups are collected in the Study Drug Administration/HemoCue/Dose Adjustment Form in the eCRF. Two types of dosing changes will be calculated.

A dose-per-intake change is the change in the number of milligrams on the intake day (for example from 200 mg TIW to 250 mg TIW). A weekly-dose change is the change in the prescribed weekly dose, calculated as the dose-per-intake times the weekly frequency.

For example a change from 200 TIW to 250 TIW is a change of 600 mg to 750 mg per week which is considered as a change in dose-per-intake and a change in weekly-dose as well.

For each subject the total number of dose-per-intake changes and the weekly-dose changes will be calculated.

9.1.2 Duration of Exposure

Exposure time will be categorized according to the following categories by treatment groups (roxadustat and ESA):

- Less than 2 weeks
- At least 2 weeks, less than 4 weeks
- At least 4 weeks, less than 26 weeks
- At least 26 weeks, less than 52 weeks
- At least 52 weeks, less than 78 weeks
- At least 78 weeks, less than 104 weeks
- At least 104 weeks, less than 130 weeks
- At least 130 weeks, less 156 weeks
- More than 156 weeks
- Unknown

